9.4.3.3. Secondary analyses

In case analysis of the primary endpoints leads to rejection of null hypotheses, the following key secondary endpoints will be tested in a conditional sequential manner to show superiority of cenegeerin versus control (at alpha one-sided 0.025) according to the following ranking:

1. Change from baseline in Schirmer I test (without anesthesia) at week 8;
2. Change from baseline in SANDE scores for severity at week 12;
3. Change from baseline in SANDE scores for frequency at week 12;
4. IDEEL modules (Quality of Life [27 questions], Dry eye Treatment satisfaction & Bother [10 questions], and Dry eye Symptom bother [20 questions]) at week 12 and at week 4 (in this order);
5. Change from baseline in Cornea and conjunctiva vital staining with fluorescein NEI scales at week 4, week 8 and at week 12 (in this order);
6. Change from baseline in TFBUT at week 4, week 8 and at week 12 (in this order).

This hierarchical test strategy protects the family-wise false positive error rate at the overall one-sided 0.025 level.

Key secondary endpoints 1., 2., and 3. will be analyzed as detailed in section 9.4.3.1.

Changes from baseline in each IDEEL modules scale score will be analyzed using an mixed model for repeated measures (MMRM). The analyses will include the fixed, categorical effects of treatment, visit (4 levels: Weeks

4, 8, 12, 16) and treatment by visit interaction. Subject will be considered as a random effect. The covariance matrix used will be "unstructured". Comparisons versus vehicle TID will be provided using least square means at each visit and overall. Missing data will be imputed according to the questionnaire manuals.

Changes from baseline in TFBUT and Fluorescein staining (NEI scale) will be analyzed by means of an ANCOVA model adjusting by pre-defined baseline factors (site, gender, age class, corresponding baseline value). Missing data will be imputed according to MI-RD (or wash-out approach, see section 9.4.3.1).

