6.1.1 Randomization

Eligible patients will be randomized in a 1:1 ratio to either cenegegermin ophthalmic solution 20 mcg/mL TID or vehicle ophthalmic solution TID.

Randomization will be stratified by site to ensure balanced assignment across treatment groups. The stratified permuted block randomization list will be generated with a computer procedure by an independent statistician not involved in the conduct of the study.

Randomization will be performed through IRS. Each Patient Kit number will be randomly associated with a treatment group. The randomization list will be provided to the facility responsible for IMP packaging/labelling for the purpose of IMP preparation. Each randomized patient will be allocated with randomization number according to the stratified randomization list. Dropouts after randomization will not be replaced

The enrollment of patients will be scheduled in order to assure an inclusion of approximately 100 patients to ensure at least 90 patients assuming up to 10% of patients not evaluable after enrollment.

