10.1.2 Analysis details

Both co-primary endpoints will be analysed by means of MI-RD to handle missing data. Retrieved drop-out patients are defined as patients who discontinue study treatment and decide to remain in the study by following the schedule of assessments and continuing to adhere to protocol requirements. Consequently, for each primary endpoint, MI will be performed based on the subjects' allocated treatment arm and observed values (baseline and intermediate) as covariates in a regression model using data from Retrieved drop-out patients that have the primary endpoint assessment done.

10.1.2.1 Schirmer I test $>10\text{mm}/5\text{min}$ at week 4

This primary endpoint will be analyzed by means of a logistic regression model adjusting by pre-defined baseline factors (gender, age class, baseline Schirmer I test value as fixed effects and site as random effect) and a one-sided test will be used to test for differences between treatment groups.

For the imputation of missing data of Schirmer I test, a regression model will be created by including the baseline Schirmer I test value, gender, age class, and Schirmer I test at week 2. Two hundred data sets will be generated, and the random seed number will be 820520. MI will be implemented in the following steps:

1. Partial imputation assuming Missing at Random (MAR) will be carried out to impute intermittent (non-monotone) missing data of Schirmer I test up to week 4 based on a

multivariate joint Gaussian imputation model using the Markov chain Monte Carlo (MCMC) method. A separate imputation model will be used for each treatment arm. In case of non-convergence or non-estimability issues, a single imputation model will be considered (with treatment arm added as explanatory variable to the model). A total of 200 datasets will be created. These datasets will be utilized in Step #2.

2. The remaining monotone missing data will be imputed using a MI regression including the same explanatory variables of the previous step. According to MI-RD approach, only non-missing values from retrieve dropouts will be used to inform the regression model.
3. Each of the 200 imputed datasets will be analyzed using observed and imputed data. Rubin's rule will be used for combining results to draw inference.

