If there are not enough retrieved dropouts for convergence of MI-RD regression model, a reference-based Multiple Imputation (MI) approach will be adopted to consider a missing not at random (MNAR) mechanism for missing data: imputation of values in the rhNGF arm (above step #2) will be done using the non-missing values from the control group (this approach will be referred as "Copy Reference"). This approach does not assume benefits for rhNGF in case of discontinuation and limits a post-discontinuation clinical effect to that of vehicle. The final decision on the use of the MI-RD vs Copy-Reference for this endpoint will be done at the time of the analysis and reported in the CSR.

Whether for MI-RD or Copy-Reference approach, the adjusted estimated treatment differences in proportions between cenegegermin and vehicle at week 4 will be displayed together with the corresponding two-side 95% confidence intervals and p-value.

10.1.2.2 Change from baseline in the global SANDE score at week 12

This co-primary endpoint will be analyzed by means of an Analysis of Covariance (ANCOVA) adjusting by pre-defined baseline factors (gender, age class, baseline global SANDE score as fixed effects and site as random effect) and a one-sided test will be used to test for differences between treatment groups. Rules for derivation of SANDE scores are reported in section 12.2.

For the imputation of missing data, a regression model will be created by including the baseline global SANDE score, gender, age class, and intermediate global SANDE scores up to week 12. Two hundred data sets will be generated, and the random seed number will be 37103939. MI will be implemented in the following steps:

1. Partial imputation assuming MAR will be carried out to impute intermittent (non-monotone) missing data of global SANDE score based on a multivariate joint Gaussian imputation model using the MCMC method. A separate imputation model will be used for each treatment arm. In case of non-convergence or non-estimability issues, a single imputation model will be considered (with treatment arm added as explanatory variable to the model). A total of 200 datasets will be created. These datasets will be utilized in Step #2.
2. The remaining monotone missing data will be imputed using a MI regression including the same explanatory variables of the previous step. According to MI-RD approach, only non-missing values from retrieve dropouts will be used to inform the regression model.

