10.2.2.1 Schirmer I test >10mm/5min at week 8

The proportion of patients reaching a value of Schirmer I test (without anesthesia) >10mm/5min at week 8 will be analyzed as described in section 10.1.2.1 for the primary efficacy endpoints.

10.2.2.2 Change from baseline in SANDE score for severity at week 12

The change from baseline in SANDE score for severity at week 12 will be analyzed as described in section 10.1.2.2 for the primary efficacy endpoints.

10.2.2.3 Change from baseline in SANDE scores for frequency at week 12

The change from baseline in SANDE score for frequency at week 12 will be analyzed as described in section 10.1.2.2 for the primary efficacy endpoints.

10.2.2.4 Change from baseline in IDEEL modules (Quality of Life, Dry eye Treatment satisfaction & Bother, and Dry eye Symptom bother) at week 12 and at week 4

Rules for derivation of IDEEL scores are reported in section 12.3. The change from baseline of each IDEEL module will be analyzed by means of an MMRM adjusting by pre-defined factors (gender, age class, IDEEL module baseline value, treatment, visit, and treatment by visit interaction; subject will be considered as a random effect). The covariance matrix used will be "unstructured". Comparisons versus vehicle TID will be provided using least square means at each visit and overall and a one-sided test will be used to test for differences between treatment groups.

For the imputation of missing data, a regression model will be created by including the baseline value, gender, age class, and intermediate scores up to week 12. Two hundred data sets will be

generated, and the random seed number will be 225670. MI will be implemented in the following steps:

1. Partial imputation assuming MAR will be carried out to impute intermittent (non-monotone) missing data of IDEEL module score based on a multivariate joint Gaussian imputation model using the MCMC method. A separate imputation model will be used for each treatment arm. In case of non-convergence or non-estimability issues, a single imputation model will be considered (with treatment arm added as explanatory variable to the model). A total of 200 datasets will be created. These datasets will be utilized in Step #2.
2. The remaining monotone missing data will be imputed using a MI regression including the same explanatory variables of the previous step. According to MI-RD approach, only non-missing values from retrieve dropouts will be used to inform the regression model.

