3. Each of the 200 imputed datasets will be analyzed using observed and imputed data. Rubin's rule will be used for combining results to draw inference.

If there are not enough retrieved dropouts for convergence of MI-RD regression model, a Copy Reference approach will be adopted to consider a MNAR mechanism for missing data. The final decision on the use of the MI-RD vs Copy-Reference for this endpoint will be done at the time of the analysis and reported in the CSR.

Whether for MI-RD or Copy-Reference approach, the adjusted estimated treatment differences in means for IDEEL module scores between cenegeimin and vehicle at each available timepoint will be displayed together with the corresponding two-side 95% confidence intervals and p-value.

10.2.2.5 Change from baseline in Cornea and conjunctiva vital staining with fluorescein NEI scale at week 4, week 8 and at week 12

Rules for derivation of NEI scores are reported in section 12.4. The change from baseline in Cornea and conjunctiva vital staining with fluorescein NEI scale will be analyzed by means of an MMRM adjusting by pre-defined factors (gender, age class, NEI scale baseline value, treatment, visit, and treatment by visit interaction; subject will be considered as a random effect). The covariance matrix used will be "unstructured". Comparisons versus vehicle TID will be provided using least square means at each visit and overall and a one-sided test will be used to test for differences between treatment groups.

For the imputation of missing data, a regression model will be created by including the baseline value, gender, age class, and intermediate scores up to week 12. Two hundred data sets will be generated, and the random seed number will be 240550. MI will be implemented in the following steps:

1. Partial imputation assuming MAR will be carried out to impute intermittent (non-monotone) missing data of NEI scale score based on a multivariate joint Gaussian imputation model using the MCMC method. A separate imputation model will be used for each treatment arm. In case of non-convergence or non-estimability issues, a single imputation model will be considered (with treatment arm added as explanatory variable to the model). A total of 200 datasets will be created. These datasets will be utilized in Step #2.

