2. The remaining monotone missing data will be imputed using a MI regression including the same explanatory variables of the previous step. According to MI-RD approach, only non-missing values from retrieve dropouts will be used to inform the regression model.
3. Each of the 200 imputed datasets will be analyzed using observed and imputed data. Rubin's rule will be used for combining results to draw inference.

If there are not enough retrieved dropouts for convergence of MI-RD regression model, a Copy Reference approach will be adopted to consider a MNAR mechanism for missing data. The final decision on the use of the MI-RD vs Copy-Reference for this endpoint will be done at the time of the analysis and reported in the CSR.

Whether for MI-RD or Copy-Reference approach, the adjusted estimated treatment differences in means for NEI scale scores between cenegeamin and vehicle at each available timepoint will be displayed together with the corresponding two-side 95% confidence intervals and p-value.

10.2.2.6 Change from baseline in TFBUT at week 4, week 8 and at week 12

The change from baseline in TFBUT values will be analyzed by means of a MMRM adjusting by pre-defined factors (gender, age class, TFBUT baseline value, treatment, visit, and treatment by visit interaction; subject will be considered as a random effect). The covariance matrix used will be "unstructured". Comparisons versus vehicle TID will be provided using least square means at each visit and overall and a one-sided test will be used to test for differences between treatment groups.

For the imputation of missing data, a regression model will be created by including the baseline value, gender, age class, and intermediate scores up to week 12. Two hundred data sets will be generated, and the random seed number will be 101149. MI will be implemented in the following steps:

1. Partial imputation assuming MAR will be carried out to impute intermittent (non-monotone) missing data of TFBUT values based on a multivariate joint Gaussian imputation model using the MCMC method. A separate imputation model will be used for each treatment arm. In case of non-convergence or non-estimability issues, a single imputation model will be considered (with treatment arm added as explanatory variable to the model). A total of 200 datasets will be created. These datasets will be utilized in Step #2.

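### The SAP drops site, the only randomisation stratum, from the NEI and TFBUT models without declaring it, and the IDEEL model lacks it too; if site matters after baseline adjustment, these tests are somewhat conservative.

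*SAP*

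**What the plan says.** - **Design.** SAP 6.1.1: "Randomization will be stratified by site to ensure balanced assignment across treatment groups". Protocol 4.4 agrees, and no other stratification factor is named.
- **Protocol model for NEI and TFBUT** (9.4.3.3): "ANCOVA model adjusting by pre-defined baseline factors (site, gender, age class, corresponding baseline value".
- **Protocol model for IDEEL** (same section), an MMRM: "The analyses will include the fixed, categorical effects of treatment, visit", and the treatment-by-visit interaction, with subject as a random effect. Site is not listed.
- **SAP models**, all MMRMs with a random subject effect and an unstructured covariance:
  - NEI (10.2.2.5): "gender, age class, NEI scale baseline value, treatment, visit, and treatment by visit interaction"
  - TFBUT (10.2.2.6): "gender, age class, TFBUT baseline value, treatment, visit, and treatment by visit interaction"
  - IDEEL (10.2.2.4): "gender, age class, IDEEL module baseline value, treatment, visit, and treatment by visit interaction"
- **SAP co-primary models**, which keep site: "gender, age class, baseline Schirmer I test value as fixed effects and site as random effect" for Schirmer (10.1.2.1) and "gender, age class, baseline global SANDE score as fixed effects and site as random effect" for SANDE (10.1.2.2). Key secondary endpoints 1 to 3 inherit it by cross-reference.
- **SAP 7.9**, the list of changes from the Protocol, describes the MMRM as a clarification and an extension of ANCOVA. It does not mention site.

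**The concern.** An extension of the Protocol's ANCOVA would be expected to carry over its covariates. Gender, age class and baseline were carried over for NEI and TFBUT; site was not, and a reader of SAP 7.9 would not learn this. The SAS code in the appendix covers only the co-primary models, so it does not settle the matter.

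Blocked randomisation within site balances the arms within site, which makes the treatment contrast more precise when sites differ. A model without site leaves the between-site variance in its error term and reports a standard error larger than the true one. What is at stake is power in the fixed sequence of SAP 10.2: steps 5.1-5.3 (NEI) and 6.1-6.3 (TFBUT), and steps 4.1-4.6 (IDEEL) for the same design reason. A miss at any step closes all later ones.

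**Working it through.** **1. The plan's own figures.** The plan states no power for NEI, TFBUT or IDEEL. The co-primary figures in SAP section 5 reproduce with 45 patients per arm and one-sided alpha 0.025: Schirmer 35% vs 5%, pooled variance, 95.8%; SANDE difference 15, SD 20, t-test, 94.0%; product 0.958 x 0.940 = 0.90. They do not depend on this point, because those models keep site.

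**2. Side by side.**

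| Endpoint | Protocol 9.4.3 | SAP 10.1-10.2 | Declared in SAP 7.9? |
|---|---|---|---|
| Schirmer and SANDE (co-primary) | site | site, random | not removed |
| NEI, TFBUT | ANCOVA with site | MMRM without site | MMRM yes, loss of site no |
| IDEEL | MMRM without site | MMRM without site | not removed |

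**3. Direction, without a baseline covariate.** Assumptions, none of them in the documents: one visit, 10 equal sites of 9 patients (the Protocol says about 10 sites and 90 evaluable patients), permuted blocks of 4, total SD 1, site fitted as a fixed factor, and an effect of 0.6 SD for power.

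| Site ICC | Model SE without site | True SE | One-sided type I error without site | Power without / with site |
|---|---|---|---|---|
| 0 | 0.210 | 0.211 | 0.025 | 80.1% / 79.3% |
| 0.05 | 0.210 | 0.207 | 0.021 | 80.2% / 80.9% |
| 0.10 | 0.209 | 0.202 | 0.022 | 82.1% / 84.1% |
| 0.20 | 0.209 | 0.191 | 0.015 | 83.0% / 88.2% |

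With site in the model the type I error stays at 0.024-0.027. Simulation error on these rates is about sqrt(0.025 x 0.975 / 10000) = 0.0016. Omitting site therefore errs towards conservatism.

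**4. Size, with the baseline covariate the SAP models do contain.** What matters is the ICC left after baseline adjustment. Let r be the within-site correlation between baseline and follow-up (assumed 0.3 to 0.7), with total variance 1. The SE ratio is at most about 1/sqrt(1 - residual ICC); simulated values are slightly lower, because fitting site costs degrees of freedom.

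*Site effect present equally at baseline and follow-up.* Slope b = ICC + (1 - ICC)r; residual ICC = ICC(1 - b)^2 / (1 - b^2).
- ICC 0.15, r = 0.3: b = 0.405; 0.15 x 0.354 / 0.836 = 0.064; ratio 1.03.
- ICC 0.05, r = 0.7: b = 0.715; 0.05 x 0.081 / 0.489 = 0.008; ratio 1.004.

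*Site effect arising only after baseline.* Residual ICC = ICC / [ICC + (1 - ICC)(1 - r^2)].
- ICC 0.05, r = 0.3: 0.05 / 0.9145 = 0.055; ratio 1.03.
- ICC 0.15, r = 0.7: 0.15 / 0.5835 = 0.257; ratio 1.16.

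Simulated excess of the SE without site over the SE with site (same layout as step 3, range over r):

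| Raw ICC | Present at baseline | Only after baseline |
|---|---|---|
| 0 | -0.7% to -0.5% | -0.6% to -0.5% |
| 0.05 | -0.2% to 0.7% | 2.0% to 4.0% |
| 0.10 | 0.2% to 1.7% | 4.8% to 8.7% |
| 0.15 | 0.5% to 2.9% | 7.8% to 14.0% |

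The row for ICC 0 is the price of including site needlessly: under 1% in SE.

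**The case against.** The strongest case against runs as follows.

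- **Examiner variation is already limited.** Under SAP 7.8 and 12.4, NEI uses the blinded reading centre's value whenever there is one; the site grade is only a fallback. IDEEL is completed by the patient and has no examiner. Only TFBUT, the last three steps, plainly depends on the examiner. *This stands*, and it weakens any argument from grading habits. Sites can still differ in patients, staining technique and image capture.
- **Baseline adjustment removes most of a persistent site effect.** *This stands*, and it is why the lower range is only about 0-3%. It does not cover site differences that emerge during follow-up.
- **Validity is not threatened.** *This stands.* A reader might infer that ignoring the stratum inflates false positives; the calculation shows the opposite direction.
- **IDEEL is not a departure from the Protocol.** *This stands.* A reader might infer that all three models contradict the Protocol; only NEI and TFBUT do.
- **The remedy is not quite one term.** The MMRMs already specify a random subject effect and an unstructured covariance, each fitted in 200 imputed data sets, so a site component needs a fallback rule. *This stands.*

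None of this explains why site disappeared from the NEI and TFBUT models or why SAP 7.9 is silent about it.

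**Conclusion.** For NEI and TFBUT (six steps) there is an undeclared difference in covariates between Protocol and SAP. For IDEEL (six further steps) the model does not reflect the stratified design, though it agrees with the Protocol in having no site term. The consequence is conditional: if site remains prognostic after baseline adjustment, the standard errors are too wide and some power is lost. The ranges of about 0-3% (effect already present at baseline) and about 2-14% (effect arising only later) rest on an assumed ICC of 0.05-0.15, an assumed baseline correlation of 0.3-0.7, equal sites, blocks of 4 and a single visit. With no site effect there is no loss.

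A reader might infer that power is certainly lost in 12 of the 15 key secondary steps, or that the omission amounts to discarding 5-15% of the sample. The documents do not support either: they give no ICC, and those sample figures equate the loss with the raw ICC, ignoring the baseline covariate. The co-primary endpoints and key secondary endpoints 1 to 3 are unaffected. The change is worth making because it is cheap and restores agreement with the design.

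**What to change.** Before unblinding:

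1. Add site as a random intercept to the NEI and TFBUT MMRMs (SAP 10.2.2.5, 10.2.2.6), as in 10.1.2.1 and 10.1.2.2, and for consistency to the IDEEL MMRM (10.2.2.4).
2. State a fallback in case the model does not converge, for example site as a fixed effect with small sites pooled by a rule set while blinded.
3. List in SAP 7.9 both the change of model and the change of covariates for each endpoint. If site was removed on purpose, give the reason there instead.

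The cost is one model term per MMRM and one fallback rule. No new data are needed, and the loss of precision is under 1% in SE if site turns out to have no effect.

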7.9 Changes in the planned analysis

The following changes have been included, compared to the protocol [1]:

- In the secondary endpoint on SANDE, the global score has been included (section 3.2.2) in addition to severity and frequency scores.
- In the explorative endpoint on SANDE, the global score has been included (section 3.2.3) in addition to severity and frequency scores.
- A clarification on the use of data from blinded reading center and site investigator has been added in section 7.8.
- The first key secondary endpoint in section 10.2.1 has been reworded in alignment with the definition of the Schirmer I test primary endpoint.
- A clarification on the use of a Mixed Model for Repeated Measurements (MMRM), extension of ANCOVA for repeated measurements, after imputation through MI-RD for IDEEL, NEI scale and TFBUT endpoints has been added in section 10.2.2, in alignment with treatment policy estimand used for primary endpoint.
- Considering the progress of data collection, the overview of planned statistical analyses (section 6.2) has been updated. A single database lock will be performed at the end of the study (instead of two locks), followed by the release of the KFR and by the final analyses. This decision represents a conservative choice in favor of the integrity of the study.

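### The MMRMs for IDEEL, NEI and TFBUT impose one baseline slope on all visits; adding baseline-by-visit is a cheap safeguard for the visit-specific tests

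*SAP*

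**What the plan says.** SAP 10.2.2.4 to 10.2.2.6 give three MMRMs of the same form, each with an unstructured covariance matrix:

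- IDEEL modules: "gender, age class, IDEEL module baseline value, treatment, visit, and treatment by visit interaction".
- NEI staining: "gender, age class, NEI scale baseline value, treatment, visit, and treatment by visit interaction".
- TFBUT: "gender, age class, TFBUT baseline value, treatment, visit, and treatment by visit interaction".

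None lists a baseline-by-visit term. The SAS code in SAP 15.5 covers only the two co-primary analyses, so it does not supply one.

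The models are fitted after imputation that uses scores up to week 12: "Each of the 200 imputed datasets will be analyzed using observed and imputed data".

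Protocol 9.4.3.3 treated the endpoints differently. NEI and TFBUT, ranked for testing at weeks 4, 8 and 12, were to be analysed by an "ANCOVA model adjusting by pre-defined baseline factors (site, gender, age class, corresponding baseline value"). IDEEL was already to be analysed by an MMRM, with treatment, visit and treatment-by-visit listed and no baseline covariate. SAP 7.9 declares the MMRM as a clarification and calls it an "extension of ANCOVA for repeated measurements, after imputation through MI-RD for IDEEL, NEI scale and TFBUT endpoints".

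**The concern.** With treatment-by-visit in the model, each visit has its own treatment effect. With a single baseline term, every visit must share one baseline slope. The fitted slope is then a weighted compromise. Where a visit's true slope differs from it, the adjustment at that visit is inexact. Residual variance is left in the standard error, and part of any chance baseline difference stays in the estimate.

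A per-visit ANCOVA does not have this restriction, so for NEI and TFBUT the SAP model is narrower than the one it replaces. The restriction is not a price paid for handling missing data, because the data to week 12 are complete in each imputed set before the model is fitted.

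The key secondary tests form a fixed sequence of 15 (SAP 10.2.2). Twelve use these MMRMs, and five of those are at week 12: 4.1, 4.2, 4.3, 5.3 and 6.3. Week 12 comes eight weeks after treatment ends. If the models run over weeks 4, 8 and 12, it is also an end visit, where a common slope fits worst when the relation drifts steadily.

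**Working it through.** **The plan's own figures.** The documents give no power or precision figure for IDEEL, NEI or TFBUT. The co-primary powers do reproduce with 45 per arm (Schirmer 95.8%, SANDE 94.0%, product 0.958 × 0.940 = 90.05%), but they do not bear on this point.

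**Inputs.**
- From the documents: 45 evaluable patients per arm, one-sided alpha 0.025, complete data after imputation, unstructured covariance.
- Assumed, because the documents give none: correlations of the score with baseline at weeks 4/8/12 and between visits, with equal variances (baseline SD = 1).
- Left out for simplicity: gender, age class, site and Rubin pooling.

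**Formula.** For change from baseline, the true slope at visit j is b_j = r_j − 1, where r_j is the correlation with baseline. The residual variance is 1 − r_j². With treatment-by-visit in the model, the estimate at visit j is the raw difference in means minus the common slope b_c times the baseline difference. Relative to a visit-specific slope:

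variance ratio = 1 + (b_j − b_c)² / (1 − r_j²); SE ratio = its square root.

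b_c is the generalised least squares slope, iterated with the unstructured covariance.

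**Worked case.** Correlations 0.7/0.55/0.4; between-visit correlation 0.7 for adjacent visits and 0.7² = 0.49 two visits apart. Then b_c = −0.397 and b_12 = −0.600. The difference is −0.203, and its square is 0.0412. Dividing by 1 − 0.16 = 0.84 gives 0.049. The variance ratio is 1.049 and the SE ratio 1.024.

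**Range at week 12.** The power column is Φ(2.80/SE ratio − 1.96), for a test with 80% power under visit-specific slopes.

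| Baseline correlation, weeks 4/8/12 | Between-visit correlation | b_12 − b_c | SE ratio | Power |
|---|---|---|---|---|
| 0.6/0.6/0.6 | any | 0 | 1.000 | 80% |
| 0.6/0.5/0.4 | 0.7, decaying | −0.120 | 1.009 | 79.3% |
| 0.6/0.4/0.3 | 0.6, equal | −0.191 | 1.020 | 78.4% |
| 0.7/0.55/0.4 | 0.7, decaying | −0.203 | 1.024 | 78.1% |
| 0.7/0.5/0.3 | 0.5, decaying | −0.260 | 1.036 | 77.1% |
| 0.7/0.5/0.3 | 0.7, equal | −0.382 | 1.077 | 73.9% |

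**Simulation check** (2,000 trials per scenario, 45 per arm):
- 0.7/0.55/0.4: variance ratio 1.05; power 76.7% with the common slope against 79.2% with baseline-by-visit.
- 0.6/0.6/0.6: variance ratio 0.99; power 78.4% against 77.7%. This is the whole price of the extra term when it is not needed.
- 0.8/0.5/0.2, a deliberately extreme case: variance ratio 1.20; power 70.9% against 79.4%.
- The mean treatment estimate matched the true effect in every scenario under both models.

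**Chance imbalance.** The share carried into the week-12 estimate is b_12 − b_c. The standard error of a baseline difference is √(2/45) = 0.21 SD, so 0.2 SD is an ordinary imbalance. It shifts the week-12 difference by 0.12 × 0.2 = 0.02 SD in the mildest unequal case above, and by 0.382 × 0.2 = 0.08 SD in the steepest.

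**Other visits.** In the worked case the variance ratio is 1.018 at week 4 and 1.004 at week 8. If week 16 is also modelled, with correlations 0.7/0.6/0.5/0.4 and decaying between-visit correlation, the week-12 variance ratio is only 1.01 to 1.02.

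**The case against.** The case for leaving the model alone is substantial.

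- **The drift is an assumption.** No document gives a baseline correlation for any visit. A reader might infer that the correlation falls after treatment and that week 12 is therefore over-adjusted. The design also allows the opposite: both arms use the same artificial tears from week 5 to week 12, and scores may return towards each patient's untreated level. With correlations rising 0.4/0.5/0.6, the week-12 SE increases by only 0.3–0.6%, the model under-adjusts there, and the larger cost (0.8–1.1%) moves to week 4. This stands: neither direction nor size can be stated as fact.
- **IDEEL has no ANCOVA comparator.** A reader might infer that all three endpoints lose something the protocol had. For IDEEL the SAP adds a baseline covariate that the protocol did not list. This stands, and IDEEL supplies six of the 12 MMRM tests.
- **The reach is limited.** A reader might infer that 12 of 15 tests are materially weakened. The larger losses computed for falling correlations are at week 12, which is five tests. Of these, only 5.3 and 6.3 replace a protocol ANCOVA, and 6.3 is last in the sequence, so a miss there stops nothing.
- **The model is valid and prespecified.** A main-effect baseline in an MMRM is a legitimate choice, and SAP 7.9 discloses the move to MMRM. This stands. SAP 7.9 does not, however, disclose that the baseline adjustment becomes more restrictive than the protocol's for NEI and TFBUT.

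**Conclusion.** The point holds as a minor improvement. The three MMRMs constrain the baseline slope to be equal across visits, and the imputed data give no reason to accept that constraint. For NEI and TFBUT the model is more restrictive than the protocol's ANCOVA; for IDEEL the protocol sets no such standard.

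The cost depends on correlations the documents do not give. At week 12 the SE rises by 0% if slopes are equal, about 1–2% for a moderate fall and about 4–8% for 0.7/0.5/0.3. Only a steeper fall would cost more.

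It would be wrong to conclude that baseline adjustment is lost or the tests are invalid. Baseline stays in every model, the treatment estimate is unbiased over randomisation, and no type I error problem is shown. What remains is some possible imprecision and a partial dependence on chance imbalance.

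**What to change.** Add baseline-by-visit to the MMRMs in SAP 10.2.2.4, 10.2.2.5 and 10.2.2.6. For NEI and TFBUT, keeping the protocol's ANCOVA at each tested week is an equally good alternative.

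The cost is one model term: two degrees of freedom with three modelled visits, or three with four, out of about 90. If the slopes are in fact equal, the loss is negligible (77.7% against 78.4% power in the simulation). The SAP should also list the visits in each model, since this fixes the number of slopes.

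The added term does not by itself recover the full protocol ANCOVA. That model also adjusted for site, which the SAP's NEI and TFBUT models do not list, and its gender and age-class effects were free at each visit. If equivalence to the protocol is intended, those terms need the same attention, or SAP 7.9 should record the difference.
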